5.11.2 Exploratory Efficacy Analysis

5.11.2.1 Other SUV metrics

The other SUV endpoints, SUVmean and SUVmax, will be summarized in a similar manner as the primary endpoint including observed change, LS mean and box plots.

5.11.2.3 Patient-Reported Outcome (PRO): a VAS for Cough Severity

Observed cough VAS score and change from baseline in cough VAS score will be summarized using descriptive statistics by treatment groups and visit for the ITT Population. All collected VAS data will be listed.

5.11.3 Exploratory Pharmacokinetic/Pharmacodynamics Analysis

5.11.3.1 Pharmacokinetics

Blood samples for determination of total and unbound PLN-74809 concentrations will be collected at predose (0 h), and at 2, 4, and 6 hours post dose on Day 1 and at predose and at least 2 hours postdose on Weeks 4 and 12. Concentration-time data will be tabulated by Day/Week and nominal time using descriptive statistics. All BLQ values will be presented as “BLQ” in the concentration listings. For presentation of the individual data and summary statistics, concentrations BLQ will be set to zero.

Individual participant and mean plasma concentration-time data will be presented graphically on linear and semi-logarithmic scales. Mean data will be plotted using nominal sample times, and individual data will be plotted using actual times. Concentrations collected outside the sampling time window will be excluded from PK analysis and may be excluded from summary statistics.

PK parameters for PLN-74809 (total and unbound) will be calculated as described in Section 5.2.17 and summarized using descriptive statistics.

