7.9 Pharmacokinetic Assessments

On Day 1, total and unbound plasma samples for PLN-74809 PK analysis will be obtained predose and at 2, 4, and 6 hours postdose.

At steady-state, total and unbound plasma samples for PLN-74809 PK analysis will be obtained predose and at least 2 hours postdose at Weeks 4 and 12, as indicated in the Schedule of Events ([Appendix 1](#)). Samples will be obtained and stored as detailed in the study manual.

The actual collection time of each sample, as well as the dosing time, must be recorded in the source data and on the eCRF. If the participant discontinues the study early, a plasma sample for PK should be taken at the ET visit if possible.

Aliquots of these PK samples may be used to measure nintedanib and/or pirfenidone concentrations in those participants who are receiving background SoC.

If participants experience treatment-emergent elevations in liver enzymes or ECG abnormalities, additional PK samples will be collected at the time of repeat laboratory or ECG testing (See [Sections 9](#) and [10](#)).

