DL_{CO} = diffusing capacity for carbon monoxide; ECG = electrocardiogram; EoS = end of study; ET = early termination; FEV1 = forced expiratory volume during the first seconds of the forced breath; FVC = forced vital capacity; MRI = magnetic resonance imaging; PET = positron emission tomography; PK = pharmacokinetic; VAS = visual analog scale

^a Visits 7 and 8 may be combined.

^b Baseline FVC to be obtained both during screening and on Day 1.

^c A historical value may be used if it has been completed within 1 month from the Baseline visit.

^d When time points for ECGs, vital sign assessment, and blood draws coincide, procedures should be carried out with blood draws last. ECGs should be collected postdose and close to the time of PK sample collection with the triplicate ECGs recorded within ~ 5 to 10 minutes. The triplicate ECGs will be averaged, and the mean values per time point (average of the 3 assessments) used to interpret the ECG tracings.

^e ECG abnormality, then PK sample will be collected.

	Screening	Treatment							EoS / ET
	Visit 1	Visit 2	Visit 3	Visit 4	Visit 5	Visit 6	Visit 7 ^a	Visit 8 ^a	Visit 9
	Day -28 to Day -1	Pre- Baseline Day -7 to Day -1	Baseline Day 1	Week 2 Day 14 (±2 days)	Week 4 Day 28 (±2 days)	Week 8 Day 56 (±3 days)	Day 84 (-7 days)	Week 12 Day 84 (±3 days)	Week 14 Day 98 (±3 days)

^f Liver function test abnormality, then PK sample will be collected.

^g Total and unbound PLN-74809 levels will be measured at the following timepoints:

Day 1: predose and 2, 4, and 6 hours postdose

Weeks 4 and 12: predose and at least 2 hours postdose

Actual PK sample collection time and dosing time will be recorded.

^h If the participant discontinues the study early, a plasma sample for PK should be taken at the ET Visit if possible.

ⁱ For participants receiving nintedanib/pirfenidone only; timed relative to PLN-74809 dosing.

^j Participants should be instructed to take study drug in the clinic on Visits 3, 5 and 8, and at the ET visit if applicable.

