5.2.17 Pharmacokinetic Parameters

Concentration-time data for total and unbound PLN-74809 will be analysed using noncompartmental methods in [REDACTED]¹ in conjunction with the internet-accessible implementation of [REDACTED]² [REDACTED]

QMD Ref. [REDACTED]	Governing QMD: [REDACTED]
Confidentiality Statement	
This document is the property of [REDACTED] without prior approval from [REDACTED]	and may not be duplicated, copied, altered or removed from company [REDACTED] or in compliance with [REDACTED]
REF: [REDACTED]	

		Controlled Quality Management Document Sponsor: Pliant Therapeutics Inc Protocol Number: PLN-74809-IPF-205
STATISTICAL ANALYSIS PLAN		

During the PK analysis, concentrations below the limit of quantitation (BLQ) up to the time of the first quantifiable concentration will be treated as zero. Embedded (values between 2 quantifiable concentrations) and terminal BLQ concentrations will be treated as “missing”. PK analysis will be performed using actual time relative to dosing. AUC will be calculated using the linear-up log-down method.

The following PK parameters will be calculated for PLN-74809 on Day 1:

- C_{max} : Maximum observed plasma concentration
- AUC_{0-6h} : AUC from the time 0 to 6 hours postdose
- T_{max} : Time to maximum observed plasma concentration
- $C_{max,ub}$: Maximum observed unbound plasma concentration
- $AUC_{0-6h,ub}$: Unbound AUC from the time 0 to 6 hours postdose

PK parameters will be summarized using descriptive statistics.

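### SAP 5.11.3.1 makes it mandatory to drop out-of-window PK samples from an analysis already run on actual times, which discards usable data and can bias AUC0-6h

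*SAP*

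**What the plan says.** **Exclusion rule.** SAP 5.11.3.1: "Concentrations collected outside the sampling time window will be excluded from PK analysis and may be excluded from summary statistics". Exclusion is compulsory for the PK analysis and optional for summary statistics.

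**Time basis and method.** SAP 5.2.17: "PK analysis will be performed using actual time relative to dosing", and "AUC will be calculated using the linear-up log-down method". The Day 1 parameters are Cmax, Tmax and AUC0-6h for total drug, plus unbound Cmax and unbound AUC0-6h. AUC0-6h is defined as "AUC from the time 0 to 6 hours postdose".

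**Sampling.** SAP 5.11.3.1 takes blood "at predose (0 h), and at 2, 4, and 6 hours post dose on Day 1". For later visits, protocol Appendix 1 has "Weeks 4 and 12: predose and at least 2 hours postdose", with no upper time limit. PK parameters are planned for Day 1 only.

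**Recorded times.** Protocol 7.9: "The actual collection time of each sample, as well as the dosing time, must be recorded in the source data and on the eCRF".

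**The window.** Neither document as supplied gives a sampling window in minutes or hours. Protocol 7.9 defers detail: "Samples will be obtained and stored as detailed in the study manual". That manual is not among the documents.

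**Displays.** SAP 5.11.3.1 tabulates and plots means by nominal time, and plots individual profiles at actual time.

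**The concern.** A sampling window protects a display that treats every sample as if it were drawn at its nominal time. It protects nothing in a non-compartmental analysis that already uses the real time. The SAP has this the wrong way round: exclusion is optional in the nominal-time summaries, where a mistimed sample misleads, and compulsory in the actual-time analysis, where it does not. A concentration may also appear in a participant's own plot and be missing from that participant's AUC.

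There is little to spare. Each Day 1 profile rests on three post-dose points, so one deletion removes a third of them, in an arm planned at 8 participants. The sample-size statement (protocol 12.2, SAP 3) names PK among the things the trial should evaluate. At stake are individual AUC0-6h values, and in some profiles Cmax, that would differ because of a deletion the method does not need.

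**Working it through.** The plan gives no figure to reproduce here. The check is an illustration of how far AUC0-6h moves when one sample is deleted and when it is kept at its actual time.

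**Inputs from the documents.** Day 1 samples at 0, 2, 4 and 6 h; linear-up log-down AUC; 8 active participants.

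**Assumed inputs.** One-compartment oral curve with unit scale; half-life 7.27, 8, 12, 24 or 50 h; absorption rate ka 0.5, 1 or 2 per hour (15 combinations); a deviation of 0.5 h. The lower half-life comes from treating the two targets in protocol 3.2 as if they were concentrations at 8 and 24 h: 16 × ln 2 / ln(2300/500) = 7.27 h. The protocol states durations at target, so this is an assumption and not a documented half-life.

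**Formulas.** ke = ln 2 / half-life. C(t) = ka/(ka − ke) × (exp(−ke·t) − exp(−ka·t)). A rising segment contributes d(a + b)/2 and a falling one d(a − b)/ln(a/b), where d is the interval and a, b are its end concentrations.

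**Worked case: half-life 24 h, ka 1.** ke = 0.02888. C(2) = 0.8326, C(2.5) = 0.8735, C(4) = 0.8985, C(6) = 0.8634.

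- On time: 0.8326 + 1.7311 + 1.7617 = 4.3254.
- 2 h sample deleted: 4 × 0.8985/2 + 1.7617 = 1.7971 + 1.7617 = 3.559. Change: 3.559/4.3254 − 1 = −17.7%.
- 2 h sample kept at 2.5 h: 1.0919 + 1.3290 + 1.7617 = 4.1825. Change: −3.3%.
- 4 h sample deleted: 0.8326 + 4 × (0.8326 + 0.8634)/2 = 0.8326 + 3.3919 = 4.2245. Change: −2.3%.
- 6 h sample deleted: the concentration is still rising from 2 h to 4 h (0.8326 to 0.8985), so there is no declining slope from which to extend to 6 h.
- 6 h sample kept at 6.5 h: C(6.5) = 0.8519; log interpolation back to 6 h gives 0.8610. The AUC is 4.3230, a change of −0.1%.

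**All 15 combinations, change against the on-time profile:**

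| Sample affected | Deleted | Kept at actual time |
|---|---|---|
| 2 h | −10.8% to −26.3% | at 2.5 h: −1.4% to −6.3%; at 1.5 h: +0.2% to +5.3% |
| 4 h | −0.4% to −4.8% | at 4.5 h: −0.1% to −0.7% |
| 6 h | not observed; log extrapolation possible in 7 of 15 (+0.4% to +2.4%) | at 6.5 h, interpolated to 6 h: 0 to −0.2% |

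Deleting the 2 h sample also lowers the observed Cmax by 0 to about 15%.

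**How often.** With an assumed chance q that any one post-dose sample is out of window, independently, the chance that at least one of the 8 × 3 = 24 active-arm samples is lost is 1 − (1 − q)^24. For q = 2%, 5% and 10% this is 38%, 71% and 92%. The documents give no value for q.

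**The case against.** The strongest defence has three parts. First, the window is not in the supplied documents. The study manual may set one wide enough that a 2 h sample drawn at 2.5 h is inside it, and then nothing is lost. Protocol 12.7.1 also allows a separate PK analysis plan, which might handle deviations differently. Second, actual-time analysis does not cure everything: a nominal 6 h sample drawn at 5 h still leaves the last hour unobserved. Third, the consequence is small, because PK is exploratory and descriptive and all values remain in the listings.

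The first part means that neither the frequency nor the size of the loss can be known from the documents. It does not justify the rule, because any window, wide or narrow, is unnecessary for an actual-time calculation. The second part stands and calls for a stated rule on reaching 6 h. The third stands and sets the weight of the point.

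A reader might infer more than the documents support:

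- **That the rule always biases AUC0-6h downward.** The effect depends on a sample being out of window and on which one it is. It is material for the 2 h sample and small for the 4 h sample.
- **That losing the 6 h sample leaves AUC0-6h at 55-57% of its true value.** That figure, at the 7.27 h half-life, is the area to 4 h over the true area to 6 h. Nothing in the SAP says the shorter area would be reported as AUC0-6h.
- **That participants will drop out of the PK population.** SAP 5.1.4 asks only for sufficient data and sets no minimum, so this cannot be shown.

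**Conclusion.** The inconsistency is real and rests on the text alone: the SAP computes PK parameters on actual times, the protocol secures those times, and the SAP then requires valid concentrations to be removed from that same analysis. The rule discards usable data from profiles of three post-dose points and can bias AUC0-6h.

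The size is conditional. Under the assumed one-compartment shapes it is about 11-26% downward if the 2 h sample is lost, against about 1-6% if that sample is kept at 2.5 h, and about 0-5% if the 4 h sample is lost. For the 6 h sample, the problem is mainly that the parameter is no longer observed.

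Impact is confined to exploratory, descriptive PK parameters. The primary SUV analysis (SAP 5.11.1) does not use them, and the planned correlations (SAP 5.11.3.4) use the Week 12 predose concentration instead of AUC0-6h. The point is worth making because correcting it costs almost nothing.

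**What to change.** Replace the exclusion sentence in SAP 5.11.3.1 with wording to this effect:

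- All concentrations with a recorded actual sampling time are kept in the non-compartmental analysis and the individual plots, at that time.
- The sampling window applies only to summaries and mean plots by nominal time. State the window in the SAP, or cite the manual section that holds it, including what it means for the open-ended Week 4 and 12 post-dose sample.
- When the last Day 1 sample is not at 6 h, AUC0-6h is obtained by interpolation to 6 h if the sample is later. If it is earlier or missing, AUC0-6h is obtained by extrapolation to 6 h, flagged in the listing, and is reported as not calculable where no declining slope exists.

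The cost is a few lines of SAP text and a minor programming change. No data collection changes, because actual times are already required. SAP 5 provides for amendments approved before database lock; after lock, the change would go into the addendum that section describes.

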5.11.3.2 Biomarker Change from Baseline

Biomarker results, PRO-C3, CTX-III_ HP, and ITGB6, will be summarized using descriptive statistics by treatment group and visit for each parameter. Actual biomarker concentration at each visit, the change from baseline and percent change from baseline will be presented. The result adjusted for dilution factor will be used in summaries and listings. Samples that were hemolyzed, received ambient or with a note indicating improper storage will be excluded from summaries and listed only. If a sample has been excluded, then the change from baseline for that sample will not be calculated.

Actual biomarker concentrations will be presented as a line plot showing the mean (\pm SD) concentration at each visit by treatment group for each parameter.

Absolute change from baseline and percentage change from baseline will be presented as a line plot showing baseline (0) and the mean (\pm SD) concentration at each post-dose visit by treatment group for each parameter.

QMD Ref: [REDACTED]		Governing QMD: [REDACTED]
Confidentiality Statement		
This document is the property of [REDACTED] without prior approval from [REDACTED]		and may not be duplicated, copied, altered or removed from company or in compliance with [REDACTED]
REF: [REDACTED]		

Controlled Quality Management Document		
	Sponsor:	Pitant Therapeutics Inc
	Protocol Number:	PLN-74809-IPF-205

Change from baseline to each visit will also be analysed for all biomarkers using an MMRM in the same manner as described in Section 5.11.2.1, except the factor for standard of care use (Y/N) will be excluded. LS means (\pm SE) for each treatment group and estimates for treatment difference compared to placebo, with corresponding SE, 95% CI and *P*-value, will be provided.

5.11.3.3 MRI Parameters

MRI parameters, contrast wash-in rate (kwashin), contrast wash-out rate (kwashout), maximum or peak enhancement (ME), and area under the curve at 60 seconds (AUC₆₀) will be summarized descriptively by treatment groups and visit for observed value and change from baseline.

5.11.3.4 Relationships Between Endpoints

The Spearman correlation will be utilized to assess the correlations between the following endpoints in each treatment group. The Spearman correlation coefficient will be presented with the *P*-value for each pair of endpoints.

- By region SUV to by region SUV using change from baseline in top quartile SUV
- Change from baseline in whole lung top quartile SUV, change from baseline in PRO-C3, change from baseline in CTX-III_HP, change from baseline in ITGB6, change from baseline in FVC (mL), change from baseline in FVC percent predicted (%), and observed PLN-74809 Week 12 pre-dose concentration (total and unbound).

Sample [REDACTED] for Spearman correlation:

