6 STUDY TREATMENTS

6.1 Description of Treatments

160 mg of PLN-74809 or matching placebo administered orally QD (2 tablets)

PLN-74809 and matching placebo will be supplied by Pliant as a tablet for oral administration. Study drug will be taken once daily at approximately 24-hour intervals.

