3 SAMPLE SIZE

QMD Ref. [REDACTED]	Governing QMD: [REDACTED]
Confidentiality Statement	
This document is the property of [REDACTED] without prior approval from [REDACTED]	and may not be duplicated, copied, altered or removed from company or in compliance with [REDACTED]
REF: [REDACTED]	

		Controlled Quality Management Document	
		Sponsor:	Pliant Therapeutics Inc
		Protocol Number:	PLN-74809-IPF-205
STATISTICAL ANALYSIS PLAN			

The sample size of approximately 12 participants (8 participants receiving 160 mg PLN-74809 and 4 receiving placebo) is expected to provide a meaningful evaluation of PLN-74809 safety, tolerability and pharmacokinetics (PK) in the target population and add to the data of approximately 21 participants planned to be evaluated at this dose level in an ongoing multicenter, dose-ranging Phase 2a study (PLN-74809-IPF-202).

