5.1.4 Pharmacokinetic (PK) Analysis Population

The PK analysis population includes all randomized participants who have sufficient PLN-74809 concentration data for PK calculation. Treatment assignment is by actual treatment.

QMD Ref: [REDACTED]	Governing QMD: [REDACTED]
Confidentiality Statement	
This document is the property of [REDACTED] without prior approval from [REDACTED]	and may not be duplicated, copied, altered or removed from company [REDACTED] or in compliance with [REDACTED]
REF: [REDACTED]	

		Controlled Quality Management Document
		Sponsor: Pliant Therapeutics Inc
		Protocol Number: PLN-74809-IPF-205

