5.3.5 P-values

P-values will be displayed to 4 decimal places. P-values <0.0001 will be presented as p<0.0001.

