5.11 Efficacy Analyses

All statistical tests will be performed using a two-tailed 5% overall significance level, unless otherwise stated. All comparisons between treatments will be reported with 95% confidence intervals for the difference.

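### Per-arm Spearman P-values cannot inform in placebo: with 4 planned participants an exact two-sided value cannot fall below 0.083, and a t approximation would overstate a perfect rank order

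*SAP*

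**What the plan says.** SAP 5.11.3.4 sets the analysis within arms: "The Spearman correlation will be utilized to assess the correlations between the following endpoints in each treatment group". It then adds: "The Spearman correlation coefficient will be presented with the *P*-value for each pair of endpoints". Two sets of pairs follow. The first is region against region, using change in top-quartile SUV. The second lists change in whole-lung top-quartile SUV, in PRO-C3, in CTX-III_HP, in ITGB6, in FVC (mL) and in FVC percent predicted, together with the Week 12 pre-dose PLN-74809 concentration, total and unbound. The section names no analysis population, and its sample code is redacted.

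SAP section 3 plans "8 participants receiving 160 mg PLN-74809 and 4 receiving placebo". The parent section, SAP 5.11, says: "All statistical tests will be performed using a two-tailed 5% overall significance level, unless otherwise stated". SAP 5.3.5 adds: "P-values <0.0001 will be presented as p<0.0001". SAP section 6 plans no multiplicity adjustment. Protocol 12.1 describes the study as exploratory, with no hypotheses tested.

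**The concern.** A rank correlation on four points has very few possible outcomes, so its P-value can take only a handful of values. The plan nevertheless asks for one for every pair in the placebo arm, under a section that sets a 5% level. If the method is exact, no placebo pair can reach that level, whatever the data show. If the method is the usual t approximation, the formula breaks down at a perfect rank order and returns zero, which the SAP's display rule turns into p<0.0001.

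What is at stake is how a table is read. A chance ordering of four placebo participants could look like strong evidence linking lung collagen uptake to a biomarker or to FVC, and relationships of that kind are among the trial's exploratory objectives.

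**Working it through.** **Inputs.** Approximately 12 participants at 2:1 (SAP sections 3 and 4); two-tailed 5% (SAP 5.11); p<0.0001 as the smallest printed value (SAP 5.3.5).

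**The plan's own figure.** 12 × 2/3 = 8 active and 12 × 1/3 = 4 placebo. This matches SAP section 3.

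**Exact method.** With n untied pairs and no association, all n! rank orders are equally likely. Two of them give |rho| = 1, so the smallest two-sided P-value is 2/n!.

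| n | n! | smallest exact P |
|---|---|---|
| 3 | 6 | 0.333 |
| 4 | 24 | 0.083 |
| 5 | 120 | 0.017 |
| 8 | 40,320 | 0.00005 |

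Allowing ties at n=4 does not lower the floor of 0.083.

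**t approximation (assumed).** t = |rho| × √[(n−2)/(1−rho²)] on n−2 degrees of freedom. At |rho| = 1 the denominator is zero, t is infinite and P = 0. Enumerating every rank order gives:

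| n | abs(rho) | exact P | t-approximation P |
|---|---|---|---|
| 3 | 1.0 | 0.333 | 0 (prints p<0.0001) |
| 4 | 1.0 | 0.083 | 0 (prints p<0.0001) |
| 4 | 0.8 | 0.333 | 0.200 |
| 5 | 1.0 | 0.017 | 0 (prints p<0.0001) |
| 5 | 0.9 | 0.083 | 0.037 |

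At n=4 only a perfect order crosses 5% under the approximation. That happens with null probability 2/24 = 8.3%, or 2/6 = 33% for a pair reduced to n=3. Such a reduction is plausible: Protocol 7.14 does not impute missed assessments, and SAP 5.11.3.2 drops compromised biomarker samples.

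**How often, if the approximation is used.** At n=4 the expected number of chance p<0.0001 results is the number of null placebo pairs divided by 12. The second list can be read in two ways:

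- Whole-lung SUV against each of the five other non-concentration endpoints: 5/12 = 0.42.
- Every pair among the six non-concentration endpoints: C(6,2) = 15 pairs, 15/12 = 1.25. This is an upper figure, because FVC in mL and FVC percent predicted are expected to rank alike. Without that pair it is 14/12 = 1.17.

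Region-to-region pairs are not counted.

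**Active arm, n=8.** The approximation declares significance at |rho| ≥ 0.714, with a true type I error of 0.058. The exact test requires |rho| ≥ 0.738, with a type I error of 0.046. Both are close to 5%.

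**Concentration pairs.** Placebo participants receive no drug, so their concentrations would be missing or all below quantification. SAP 5.11.3.1 sets the latter to zero for individual data and summaries. A constant variable has no rank correlation, so the output is not estimable.

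**The case against.** The strongest reply is that the only harmful outcome, a false p<0.0001, rests on code that cannot be seen. That code may request an exact method, and redaction is not a gap in the plan. This stands: a reader might infer that the tables will contain false strong results, and the documents do not support that. The expected counts above hold only if the approximation is used.

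If the code is exact, a floor of 0.083 is valid and conservative. It is a property of four observations and misleads no one. This also stands, but it leaves a P-value that cannot reach the plan's own level, so requiring it in placebo still serves no purpose. The conclusion therefore does not depend on which of the two methods was coded.

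A reader might also infer that the drug-concentration pairs would produce spurious placebo findings. They would not, because they return no estimate. The PK population, defined as "all randomized participants who have sufficient PLN-74809 concentration data for PK calculation", would probably exclude placebo in any case. What remains is that SAP 5.11.3.4 does not name a population; unseen code or table shells may do so.

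Finally, approximately 12 could yield five placebo participants. Then only a perfect order reaches 5% exactly (0.017), while the approximation also passes |rho| = 0.9 at 0.037 against an exact 0.083.

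**Conclusion.** The point holds and is minor. At the planned placebo size, the required P-values either cannot reach 5% (exact: floor 0.083, or 0.333 at n=3) or overstate a perfect order (t approximation: p<0.0001 for an event with 8.3% null probability, 33% at n=3). The exact floor needs only the planned four participants. The second branch also assumes the approximation and untied ranks.

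It would be tempting to extend this to the trial's conclusions or to the active arm, but neither extension is supported. Protocol 12.1 tests no hypotheses, no decision depends on these correlations, the primary endpoint is untouched, and the n=8 results are near nominal under both methods. The concentration pairs are a matter of missing detail and produce no false result.

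**What to change.** In SAP 5.11.3.4, report placebo correlations descriptively, as a coefficient and a scatter plot without a P-value. If P-values are kept, state that they are exact (permutation); that alone prevents a false p<0.0001. As a clarification only, add that pairs involving PLN-74809 concentration are computed in the PLN-74809 arm.

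The cost is two or three sentences. Any programming change cannot be sized, because the code is redacted. The downside of the first option is that no placebo P-values appear. At n=4 this gives up nothing that could have reached 5%; at n=5 it gives up only the perfect-order case (exact 0.017).
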